5.1.2 Ethiodized Oil

- Other Names: Ethiodol[®]
- Classification; Injectable radio-opaque diagnostic agent
- Drug specifics: Ethiodol[®], brand of ethiodized oil, is a sterile injectable radio-opaque diagnostic agent for use in hysterosalpingography and lymphography. It contains 37 % iodine (475 mg/ml) organically combined with ethyl esters of fatty acids (primarily as ethyl monoiodostearate and ethyl diiodostearate) of poppyseed oil. Ethiodized oil has been used widely for chemoembolization of the hepatic artery for primary and metastatic liver cancer.
- Side Effects: One of the major side effects of ethiodized oil is impairment of liver function (38). Since ethiodized oil causes ischemic changes in the liver, special attention to liver function should be considered. Visualization of the portal vein is a sign of portal reflux through sinusoids. Infusion of ethiodized oil should be stopped if the larger order portal vein branches are visualized. Another rare complication is pulmonary oil embolization, which is also seen when more than 20 ml of ethiodized oil is infused (50). In this study, the maximum dose of ethiodized oil for embolization will be 20 ml or less. Erosive gastroduodenal lesions or ischemic change in biliary ducts were reported in patients who received chemoembolization (51, 52). However, most of them are clinically insignificant and managed medically.

5.1.3 Gelatin sponge

- Other Names; Gelfoam[®], Surgifoam[®]
- Classification; Medical device for hemostasis
- Drug specifics: Absorbable gelatin sponge is a medical device intended for application to bleeding surface as a hemostatic. It is a sterile, water-insoluble, nonelastic, pliable product prepared from purified porcine skin gelatin. Gelatin sponge is usually absorbed completely in from four to six weeks, without inducing excessive scar tissues.
- Side Effects: When gelatin sponge was used during intravascular catheterization for the purpose of producing vessel occlusion, the following adverse events have been reported; fever, necrosis of specific anatomical areas, duodenal and pancreatic infarcts and abscess. Since smaller sizes of the occlusive agents cause more ischemic complications and development of collateral circulation, gelatin sponge powder will not be used in this study.

5.1.4 Ipilimumab: In this study, ipilimumab is considered investigational.

- Other Names: Anti-CTLA-4 monoclonal antibody, MDX-010 (MDX-CTLA4, Transfectoma-derived), Yervoy®
- Classification: Human monoclonal antibody, IgG1 subclass
- Mode of Action: Ipilimumab is specific for the CTLA4 antigen expressed on a subset of activated T-cells and regulatory T cells. CTLA4 interaction with the B7 molecule,

- one of its ligands expressed on professional antigen presenting cells, can down-regulate T-cell response. Ipilimumab is, thought to act by blocking the interaction of CTLA4 with the B7 ligand, resulting in a blockade of the inhibitory effect of T-cell activation.
- Storage and Stability Ipilimumab must be stored in a secure area according to local regulations. The investigator must ensure that it is stored at a temperature between 2°C to 8°C. Ipilimumab is given undiluted or further diluted in 0.9% NaCl Injection, USP or 5% Dextrose Injection, USP to a concentration between 1 mg/mL and 2 mg/mL. Undiluted or diluted ipilimumab solution is stable in a polyvinyl chloride (PVC), non- PVC/non DEHP (di-(2-ethylhexul) phthalate) IV bag or glass container up to 24 hours refrigerated at (2°C to 8°C) or at room temperature/ room light. Do not freeze. Shelf-life surveillance of the intact vials is ongoing.
- **CAUTION:** Ipilimumab does not contain antibacterial preservatives. Vials are for single use only. Use prepared IV solution immediately. Discard partially used vials.
- Dose Specifics Calculate Total Dose as follows: Patient body weight in kg x 1 mg/kg
 total dose in mg
- Preparation: The supplies needed for ipilimumab preparation and administration include calibrated syringes and infusion containers. Ipilimumab is to be administered as an intravenous infusion using an in-line filter (pore size of 0.2 micrometer to 1.2 micrometer) and a volumetric pump, at 1 mg/kg dose, to complete the infusion in 30 minutes, with a 3-mL normal saline flush at the completion of the infusion. Reduced duration of infusion as compared to the 90 minutes for 3mg/kg dosing was approved by BMS.
- As ipilimumab is stored at refrigerated temperatures (2-8°C), allow the appropriate number of vials of ipilimumab to stand at room temperature for approximately five minutes.
- Mix by GENTLY inverting several times. DO NOT shake.
- Route of Administration: Ipilimumab is administered as an IV infusion only. Infusions should be administered over 30 minutes +/- 5 minutes. Ipilimumab should be administered under the supervision of a physician experienced in the use of intravenous (IV) agents.
- Incompatibilities: No compatibility information is available.
- Availability: Ipilimumab is available in 5 mg/mL single-use vials (40 mL). The sterile solution in the vial is clear and colorless.
- Side Effects: See the BMS Comprehensive Adverse Events and Potential Risks List (CAEPR) in Section 6.2 for list of side effects
- Nursing/Patient Implications: Monitor patients for immune-related adverse events, e.g., rash/vitiligo, diarrhea/colitis, uveitis/episcleritis, hepatitis and hypothyroidism. If you suspect toxicity, refer to the protocol guidelines for ruling out other causes. Ipilimumab may be excreted in milk or cross the placenta; therefore, nursing women and women with known or suspected pregnancy should not take ipilimumab. Closely monitor patients who are on narcotics during the treatment with ipilimumab. Narcotics may mask GI signs and symptoms such as diarrhea or abdominal pain, which are relevant complications of a bowel perforation. Minor diarrhea can be a potential sign of colitis and require immediate attention.
- Handling and Disposal: As with all injectable drugs, care should be taken when handling and preparing ipilimumab. Whenever possible, ipilimumab should be prepared in a laminar flow hood or safety cabinet using standard precautions for the

- safe handling of intravenous agents applying aseptic technique. Latex gloves are required. If ipilimumab concentrate or solution comes in contact with skin or mucosa, immediately and thoroughly wash with soap and water. After final drug reconciliation, unused ipilimumab solution should be disposed at the site following procedures for the disposal of anticancer drugs.
- Ipilimumab Destruction: Partial vials can be destroyed on site per institution policy. Intact vials of the expired drug, recalled, or when protocol is closed to treatment cannot be destroyed on site without the PMB/NCI approval. If ipilimumab is to be destroyed on site, it is the investigator's responsibility to ensure that arrangements have been made for disposal and that procedures for proper disposal have been established according to applicable regulations, guidelines, and institutional procedures. Appropriate records of the disposal must be maintained.

5.1.5 Nivolumab (NSC748726): In this study, nivolumab is considered investigational.

- Other Names: BMS-936558; MDX1106; ONO-4538; anti-PD-1
- Classification: Fully humanized monoclonal antibody
- Mode of Action: Nivolumab is a fully human monoclonal immunoglobulin G4 (IgG4) antibody (HuMAb) that targets the programmed death 1 (PD-1) cell surface membrane receptor. PD-1 is a negative regulatory molecule expressed by activated T and B lymphocytes. Binding of PD-1 to its predominant ligand, PD-L1, results in the down regulation of lymphocyte activation. Loss of effective immune response to antigens expressed by tumors may be a significant factor in tumor progression. PD-L1 expression has been found on a number of tumors & may also be a mechanism by which tumors can directly engage PD-1 to evade an effective anti-tumor immune response. Inhibition of PD-1 interaction with PD-L1 promotes immune responses and antigen specific T cell responses to both foreign antigens as well as self-antigens. Nivolumab was shown to promote the proliferation of human T-cells in a variety of assays, which is an anticipated pharmacologic result of PD-1 inhibition.
- Storage and Stability: Intact vials: 2-8°C (36-46°F); Protect from light, protect from freezing; Infusion room temp: 4 hours max including infusion and up to 24 hours if refrigerated for the first 20 hours.
- Dose Specifics: The dosing calculations should be based on the actual body weight.
 If the patient's weight on the day of dosing differs by > 10% from the weight used to
 calculate the original dose, the dose must be recalculated. All doses should be
 rounded to the nearest milligram. There will be no dose modifications allowed.
- Preparation: Nivolumab is available as 100 mg vials (10 mg/mL), which include an overfill. It is supplied in 10 mL type I flint glass vials, with butyl stoppers and aluminum seals. Nivolumab injection can be infused diluted (10 mg/mL) or diluted with 0.9% Sodium Chloride Injection, USP to concentrations no less than 0.35 mg/mL.
- Route of Administration: IV using a volumetric pump with 0.22 micron pre size, low-protein binding polyethersulfone membrane in-line filter. Nivolumab should be administered over 30 minutes +/- 5 minutes. Should be administered ahead of ipilimumab on days when both to be administered
- Incompatibilities: No incompatibilities between Nivolumab injection and polyolefin bags have been observed.
- Side Effects: See the Comprehensive Adverse Events and Potential Risks List (CAEPR) in Section 6.2 for list of side effects.

- Nursing/Patient Implications: Infuse over 30 minutes +/- 5 minutes in a minimum of 60 ml infusion volume through a 0.22 micron in-line filter. Monitor carefully for infusion reactions and treat accordingly.
- Handling and Disposal: Use appropriate precaution for handling and disposal.

5.2 Dose Rationale

Patients will receive immunoembolization using GM-CSF at dose of 1500mcg every 3 weeks for the first four treatments then offered every 4 weeks maintenance. In the phase 1 dose escalation study, there was no dose-limiting toxicity up to 2,000mcg of GM-CSF dose; however, there was possible negative correlation between very high serum GM-CSF levels and PFS in patients with small liver metastasis. Therefore, our current standard care treatment uses 1,500 mcg of GM-CSF to avoid potential detrimental effects of high-dose GM-CSF.

The dosing of IPI+NIVO noted to be IPI 1mg/kg and 3mg/kg for the first four doses has been studied in a number of cancer types. It has been shown to be safe, and with less toxicity as evidenced in [NCT01454102].

Regarding the dosing of nivolumab, following the combination IPI+NIVO dosing for the first four doses the every 4-week schedule (Q4W) of NIVO will be more convenient for subjects. Based on pharmacokinetic modeling, the 480 mg Q4W (after steady state is reached with 3 mg/kg or 240 mg every 2 weeks) will provide steady-state average concentrations similar to 3 mg/kg or 240 mg Q2W, which has been shown to provide longer survival in NSCLC patients. However, 480 mg Q4W is expected to result in higher (approximately 20%) steady-state maximum concentration (peaks), and lower (approximately 10%) steady-state trough concentrations compared to steady state of 3 mg/kg Q2W. Nivolumab was adequately tolerated up to 10 mg/kg, the highest dose level tested, and no maximum tolerated dose was identified. In addition, the exposure-response relationship for safety is flat. Thus, a slight increase in the steady-state maximum concentration is not expected to increase the safety risk of nivolumab. However, a marginal decrease in steady-state trough concentration is not expected to reduce the efficacy as high trough concentrations and > 90% intra-tumoral receptor occupancy are still maintained at 480 mg Q4W dose. Nivolumab 480 mg Q4W is expected to have similar efficacy and safety profile to 3 mg/kg Q2W.

5.3 Procedure of Immunoembolization

5.3.1 Hospital Admission

Patients will be admitted to Thomas Jefferson University Hospital and undergo immunoembolization on Day #2, following IPI + NIVO on Day #1.

5.3.2 Access of the hepatic artery

An angiogram of the hepatic arteries will be obtained by the established technique. Non-ionized contrast will be used for angiographic studies to minimize the risk for allergic reactions. One of the hepatic lobes will then be treated based on the locations and sizes of the tumors. The proper arterial catheter placement, appropriate perfusion pattern to targeted tumors and existence of arteriovenous shunting that may cause pulmonary embolism by ethiodized oil will be thoroughly evaluated by angiography prior to the

embolization procedure. Such a degree of shunting is rarely ever seen in this patient population but discretion of the interventional radiologist will be used if shunting identified.

5.3.3 Embolization

For the patients who receive immunoembolization with GM-CSF, 3.5ml of Leukine® Liquid (1,500 mcg of GM-CSF) will be used. This solution will be emulsified in ethiodized oil (Ethiodol®) by repeated transfer of the two liquids between syringes connected via a stopcock. The amount of ethiodized oil administered is calculated based on tumor volume (1 ml per cm of summed tumor diameters). The actual amount of ethiodized oil will be decided based on the angiographic findings, including the degree of tumor vascularity and flow within the target hepatic artery. However, the maximum dose of ethiodized oil will not exceed 20 ml. The GM-CSF/ethiodized oil mixture will be done in the angiography suite immediately prior to the intraarterial delivery. When an emulsion has formed, the GM-CSF/ethiodized oil mixture will be slowly injected into the hepatic artery. Endpoints for the infusion of ethiodized oil will be delivery of the planned volume or the appearance of larger order portal vein branches. The perfusion pattern to the targeted tumors will be monitored during the injection of the ethiodized oil. Following this injection, gelatin sponge particles (1-2 mm size) will be infused into the hepatic artery until stasis of antegrade flow is obtained.

The immunoembolization procedure will be repeated every 3 weeks for the first 4 cycles and then if patient has shown evidence of tumor response, IEMBO may continue on maintenance every 4 weeks until disease progression or limiting toxicities. If the tumor is confined to a single lobe of the liver, embolization will be repeated to that lobe but interval between treatments may be extended up to every 6 weeks at the discretion of the treating physician. If the liver metastases are located in the both lobes of the liver, each hepatic lobe will be treated alternately. Variant arterial anatomy may require departure from this principle. Examples include a left lobe with dual supply from the left gastric artery and proper hepatic artery. The latter may be treated along with the right lobe.

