3.2 Primary Study Endpoint

1. Best hepatic response (CR + PR +SD) by response criteria (RECIST 1.1) starting at week 12

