5.4 Treatment Regimen Combination

Patients will be seen in the outpatient office on Day #1 of every cycle and receive administration of ipilimumab and nivolumab or once in maintenance phase nivolumab alone. On Day #2 they will undergo IEMBO consisting of intra hepatic artery administration of GM-CSF (1500mcg) mixed with ethiodized oil emulsion, followed by embolization of the hepatic artery with gelatin sponge particles under the care of interventional radiology. Patients will undergo this combination intervention every 3 weeks for 12 weeks unless significant disease progression, limiting toxicity, or withdrawal of consent. Interim imaging after 2 cycles will be peformed to ensure there has not been rapid progression. After four combination treatments if noted to have CR, PR, or SD patients will be offered maintenance therapy with combination intervention every 4 weeks until disease progression, limiting toxicity, or withdrawal of consent. When undergoing every 4 week maintenance patients will receive NIVO on Day #1 and IEMBO on Day #2 of each 28 day cycle.

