7.2.1 Analysis Population

The evaluable population includes all subjects enrolled who receive at least four combination treatments (IPI + NIVO + IEMBO at initial every 3 week intervals or NIVO + IEMBO if IPI dropped due to toxicity and IEMBO alone if NIVO dropped due to toxicity) and complete assessment after four treatments.

The As-treated population includes all subjects who receive any treatment and will be used to evaluate baseline characteristics as well as all secondary endpoints for safety and efficacy as the collected data allows.

7.2.2 Primary Endpoint:

The primary endpoint is the best hepatic response (CR + PR + SD) by response criteria (RECIST 1.1) after four combination treatments. The estimate of the hepatic metastasis stabilization rate will be presented with corresponding 95% confidence intervals. The method of Atkinson and Brown will be used to adjust for the two-stage design.

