9.4 Evaluation of overall response in the liver metastases

Clinical response in the liver metastases will be evaluated using CT scans or MRI of the abdomen initially following four combination treatments and then after every two IEMBO treatments. The same modality must be used for serial measurements of target lesions. The sum of the longest diameter (LD) of up to 6 target liver lesions will be used to determine response. The investigators must identify target indicator lesions and measure them prior to the first embolization as baseline. The investigators will then measure the same target lesions after every two IEMBO treatments.

The sum of the baseline LDs will be compared to the sum of LDs after every two IEMBO treatments following the scans after the first four treatments. New lesions will be defined as lesions that appear in the treated lobe(s) of the liver after the last evaluation and should be \geq 10 mm in longest diameter. Development of new lesion(s) in an untreated lobe (area) of the liver **will not** be considered as "Progressive Disease" for evaluation of liver response. These lesions will be treated in the subsequent embolization procedures and

they will be included in the evaluation for response after completion of two additional embolizations.

Target Liver Lesions	Non-Target Liver Lesions	New Liver Lesions in the treated lobes	Overall Liver Response
CR	CR	No	CR
CR	SD	No	PR
PR	Non-PD	No	PR
SD	Non-PD	No	SD
PD	Any	Yes or No	PD
Any	PD	Yes or No	PD
Any	Any	Yes	PD

To be assigned a status of CR or PR, changes in tumor measurements must be confirmed by the follow-up assessment using the same imaging test at a minimum interval of 4 weeks. The patients who have a CR or PR without confirmatory assessment will be categorized as SD. In the case of SD, follow-up measurements must have met the SD criteria at least once at a minimum interval of 4 weeks. The patients who have a SD without confirmatory assessment will be categorized as PD.

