15.0 APPENDICES

15.1 Study Schedule

Events	Screening Evaluation	Pretreat assessment	Initial IPI+NIVO	IEMBO			After 4 cycles	Subsequent NIVO	Subsequent IEMBO	Follow up Visits	Exit
TIME	Within 4 weeks prior to enrollment	Within 4 weeks prior to treatment	Day 1 of each 21 day cycle for first four	Day 2 of each 21 day cycle for first four	Day 3 of each 21 and 28 day cycle	Weekly while getting IEMBO	Appt. after first 4 cycles	Day 1 of each 28 day cycle after first four (*9)	Day 2 of each 28 day cycle after first four	Every 8 week outpatient appt after 12 weeks	Exit
Informed Consent	X										
Demographics	X										
Medical History	X	X (*4)	Χ	X			Х	Χ	X	Χ	X
Physical Exam	X	X (*4)	X	X			Х	X	X	X	Х
Performance Status	х	X (*4)	х				Х	Х	Х	Х	Х
Concomittent Medications	х	X (*4)	х				х	Х	Х	Х	х
CBC with Diff	X	X (*4)	X(*5)	X	Χ	Χ	Х	X(*5)	X		Х
PT, INR, PTT	X			X					X		
Serum Chemistry (*1)	x	X (*4)	X(*5)	x	Х	Х	х	X(*5)	Х		х
TSH		X (*4)	X(*5)			X(*7)	Х	X(*5, 7, 10)			
LDH	Х	X (*4)	X(*5)	Х	Х	Χ	Х	X(*5)	Х		Х
CRP		Х	X (10)		Х		Х	X(10)			
Pregnancy Test (*2)	х	X (*2)									
Study Blood			X (*3, 10, 11)	X(*3)	Х		х	X(*3, 5, 10, 11)	X(*3)		X(*11)
Liver Tumor Bx		X (*6)		X(*6)							
CT C/A/P	Х	X (*4)					Х			Х	X(*8)
MRI Abdomen	Х	X (*4)					Х			Х	X(*8)
CT or MRI Brain	х	X (*4)									
Tumor Measurement		х					х			Х	X(*8)
IPI+NIVO			Χ								
NIVO								Х			
IEMBO				Х					Х		
Toxicities and AEs		X (*4)	Х	Х	Х		Х	Х	Х	Х	Х

^{*1:} Comprehensive metabolic panel including total bilirubin, SGOT (AST), SGPT (ALT), alkaline phosphatase, albumin, creatinine, BUN, glucose, calcium, phosphate.

^{*2:} For females of childbearing potential and within 2 weeks of start of treatment, and on Day 1 of every cycle or (Day 2 if only receiving lembo.).

^{*3: 60} ml blood for immunologic testing prior to each cycle, 10 ml drawn before, 1 hour and at Day 3 after IEMBO for cytokines There is a 15 minute window for initial blood draw as patients are sometimes mid-transport at one hour post IEMBO.

^{*4:} Tests can be skipped if screening evaluation is performed within 4 weeks prior to scheduled treatment.

^{*5:} May be done within 3 days prior for Day 1 visit.

^{*6:} Biopsy or access to Archival tissue needed prior to treatment. Biopsy Day 2 of Cycle 2 before second Immunoembolization but may be performed one week before Cycle 2

^{*7:} Endrocrine labs will be checked one week prior to each infusion and at the next infusion.

^{*8:} If not completed within 4 weeks of Exit.

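### Response scans run on a calendar clock in some sections and a treatment-count clock in others, so permitted treatment delays change when stable disease and progression are read

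*Combined protocol and SAP*

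**What the plan says.** **Calendar clock.** Section 3.2 defines the primary endpoint as "Best hepatic response (CR + PR +SD) by response criteria (RECIST 1.1) starting at week 12". Section 6.1.4 judges stabilization after the first four cycles and equates that with 12 weeks. The schedule in section 15.1 marks CT, MRI and tumor measurement in the column headed "Every 8 week outpatient appt after 12 weeks".

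**Treatment-count clock.** Section 7.2.2 words the same endpoint differently: "The primary endpoint is the best hepatic response (CR + PR + SD) by response criteria (RECIST 1.1) after four combination treatments". Section 9.4 evaluates the liver "initially following four combination treatments and then after every two IEMBO treatments". Sections 3.1 and 6.1.5 also tie later scans to every two IEMBO treatments.

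**The first response scan has more than one count.** Section 3.1 and the Study Summary use the four IPI+NIVO doses (or NIVO alone if IPI is dropped), and four IEMBO only if both drugs are dropped. Sections 7.2.2 and 9.4 use four combination treatments. Section 9.1 names four IEMBO treatments in a sentence that breaks off.

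**What separates the clocks.** Section 5.3.3 states: "The immunoembolization procedure will be repeated every 3 weeks for the first 4 cycles". For disease in one lobe, it then says the "interval between treatments may be extended up to every 6 weeks at the discretion of the treating physician", without saying whether this covers the first four cycles, maintenance or both. Sections 3.1 and 6.3.3 allow combination treatment to be postponed by up to 10 weeks for immune-related toxicity. Section 6.1.2 allows up to 4 weeks for lost eligibility. The ±3-day window in sections 6.3.3 and 15.1 applies to treatment cycles. No window is given for response scans, and no section says which clock governs.

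**The concern.** Success includes stable disease, so the time of reading is part of the endpoint: remaining stable for longer is harder. The decision rule sets one count of successes against a single 60% versus 80% contrast, which presumes that success means the same thing in every patient. If the reading time moves with the treatment interval, the observed rate partly reflects how many patients had single-lobe disease or a toxicity break.

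Progression is dated when a scan detects it, so wider gaps also lengthen measured hepatic and systemic PFS without any change in the disease. With no governing clock, the scan that decides a patient's status could be chosen after the data are seen.

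**Working it through.** **1. The plan's own design figures.** Inputs (Study Summary, sections 7.1 and 7.2): stop if 8 or fewer of 13 succeed; claim efficacy if 26 or more of 35 succeed; rates 60% and 80%.

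P(claim) = Σ over x = 9 to 13 of Bin(x; 13, p) × P(Bin(22, p) ≥ 26 − x).

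- p = 0.60: type I error 0.0499; probability of stopping early 0.647.
- p = 0.80: power 0.808.

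These agree with the stated 5%, 0.65 and 80%.

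**2. Scan times under the treatment count.** The maintenance interval is from section 5.4: "When undergoing every 4 week maintenance patients will receive NIVO on Day #1 and IEMBO on Day #2 of each 28 day cycle".

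| Situation | Arithmetic | Scan time | On schedule |
|---|---|---|---|
| First response scan, on schedule | 4 × 3 | week 12 | week 12 |
| Later gap, on schedule | 2 × 4 | 8 weeks | 8 weeks |
| Later gap, single lobe at 6 weeks | 2 × 6 | 12 weeks | 8 weeks |
| First scan, one 4-week postponement | 12 + 4 | week 16 | week 12 |
| First scan, one 10-week postponement | 12 + 10 | week 22 | week 12 |
| Later gap, one 10-week postponement | 8 + 10 | 18 weeks | 8 weeks |
| First scan, 6-week intervals in induction and an IEMBO or strict combination count | 4 × 6 | week 24 | week 12 |

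The week-22 row holds under either the dose count or the combination count, because the postponement delays the whole combination. The week-24 row needs both conditions named in it. If the scan comes 3 weeks after the fourth IEMBO, it is 3 × 6 + 3 = week 21.

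**3. PFS.** If progression falls evenly within a scan gap, mean detection delay is half the gap: 12/2 − 8/2 = 2 extra weeks for 12-week gaps, and 18/2 − 8/2 = 5 extra weeks within one 18-week gap.

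**4. Illustration for power.** The documents give neither the share of patients read late nor the hazard; both are assumed here. Under constant hazard, a stable fraction p at the planned reading becomes p^(late time / planned time). A share f is read late, so the overall rate is (1 − f)p plus f times the late fraction. The step 1 formula is then applied, starting from p = 0.80 for power and p = 0.60 for type I error, with f = 10%, 20% and 30%.

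| Reading compared | Late fraction if p = 0.80 | Power | Type I error |
|---|---|---|---|
| Week 24 v 12 | 0.80^2 = 0.640 | 0.741 / 0.666 / 0.586 | 0.0272 / 0.0139 / 0.0066 |
| Week 22 v 12 | 0.80^(22/12) = 0.664 | 0.752 / 0.690 / 0.623 | 0.0296 / 0.0167 / 0.0090 |
| Confirmed SD, week 28 v 16 | 0.80^(28/16) = 0.677 | 0.758 / 0.702 / 0.642 | 0.0309 / 0.0184 / 0.0105 |

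The third row adds the 4-week confirmation of stable disease required by section 9.4 to weeks 12 and 24. Power across the rows runs from 0.59 to 0.76, against 0.81 with no late readings.

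**The case against.** **The stronger reading.** A reader might infer that single-lobe patients are first assessed at week 24, twice the planned time. The documents do not establish this. Section 3.1 triggers the first response scan on the IPI+NIVO doses, and section 5.3.3 extends only the embolization interval, so a single-lobe patient with on-time infusions would be scanned near week 12. Section 7.2.1 describes the combination treatments as given at 3-week intervals, and section 15.1 places induction IEMBO in 21-day cycles. The four-IEMBO wording in section 9.1 looks like a fragment of the section 3.1 clause. Twice is not a ceiling either: 18 weeks against 8 is 2.25 times.

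**Calendar figures as shorthand.** Week 12 and 8 weeks may simply restate four 3-week and two 4-week cycles. That is plausible, but the text does not say so, and it leaves open what happens off schedule.

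**Limits on delay.** The 10-week hold is only for immune-related toxicity, not for any cycle. That stands.

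**Rationale for counting treatments.** Bilobar disease is treated one lobe at a time, so two IEMBO treatments cover both lobes. Section 9.4 judges new lesions in an untreated lobe after two further embolizations, and the version 6 history shows the two-IEMBO rule was deliberate. This has weight for bilobar disease, but it does not cover the single-lobe patients to whom the 6-week interval applies.

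**Consequences.** PFS is a secondary Kaplan-Meier estimate in one arm, with no planned comparison. Late reading also lowers type I error, so it works against a false claim of efficacy. Both points stand and temper the concern.

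**A bare week-12 landmark would not do.** It would conflict with best response, the confirmation rule in section 9.4, and the requirement in section 7.2.1 for four treatments and an assessment after them.

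**Conclusion.** The concern holds as an unresolved conflict between two assessment clocks, with no scan window and no rule on which governs. Three sizes follow from the protocol's own figures: later scans 12 rather than 8 weeks apart with 6-week IEMBO intervals, and, with one 10-week postponement, a first response scan at about week 22 instead of 12 or a later gap of 18 instead of 8 weeks. Week 24 is conditional on 6-week intervals in induction and on a four-IEMBO or strict four-combination count.

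A reader might take the power figures as the trial's expected loss. They are not: they rest on a constant hazard and assumed shares of 10% to 30%, and the documents support neither. They show only that the direction is toward lower power, with lower type I error as well. The matter should be settled before analysis because it affects what counts as a success and when progression is dated.

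**What to change.** Reconcile sections 3.1, 3.2, 6.1.4, 6.1.5, 7.2.1, 7.2.2, 9.1, 9.4 and 15.1, and the matching Study Summary text, on one assessment clock:

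- Perform response scans at week 12 and then every 8 weeks from first dose (the section 15.1 schedule), whatever the treatment delays, with a stated window.
- State which scan starts the best-hepatic-response assessment. Keep the best-response definition and the 4-week confirmation rule in section 9.4.
- State how a patient who has not had four treatments by week 12 is counted, and align the evaluable population in section 7.2.1 and the replacement rule in section 4.3.3 with that.
- Say how the section 9.4 rule on new lesions in an untreated lobe is applied at a calendar scan, and complete the broken sentence in section 9.1.

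The change is to wording only. It alters no dose or treatment interval. Which phases the 6-week IEMBO interval covers is for the investigators to clarify. The cost is a few additional scans in delayed or single-lobe patients.
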